## PHASE 1:

Phase 1 recruitment was completed in May and June 2018. These participants are finishing out their study procedures using the below protocol (approved on 03.07.18). Based on learnings from Phase 1, we are submitting minor protocol changes for Phase 2 section below.

The goal of Phase 1 of the study is to pilot the tailored intervention for dual users of cigarettes and e-cigarettes with 10 tobacco helpline callers. The primary goal of the treatment is for participants to completely stop cigarette smoking. We will use the data and feedback we collect to make improvements to the treatment intervention and study procedures, if needed.

### **Recruitment, Consent, Baseline:**

We are requesting a Waiver of HIPAA Authorization to identify eligible participants among enrollees in the Oklahoma Tobacco Helpline. Research staff will contact eligible participants to invite them to join the study.

Interested and eligible participants will be screened, consented, and take a baseline questionnaire over the telephone. Participant responses will be recorded in password protected electronic systems. Because recruitment, intervention delivery, and follow-up is all conducted over the phone, electronically, or through mailed materials (no in person contact or materials that participants return to the study team), we are not collecting a signed consent or HIPAA Authorization.

- Recruitment, consent and baseline for Phase 1 of the Study will be conducted by the research staff (Grant Manager (GM) and Research Assistant (RA)).
- Participants will call into the Oklahoma Tobacco Helpline (OKHL) and enroll into the Helpline for Coaching Services.
- The Research Assistant (RA) will pull a report that will capture initial eligibility criteria based on standard information gathered during enrollment into the Oklahoma Tobacco Helpline and the initial coaching call.
  - Eligibility Criteria:
    - Requested Coaching Services
    - Currently using E-Cigarettes
    - English Speaking
    - 18+ years old
    - Not Pregnant
    - Not planning pregnancy in next 3 months
    - Currently using cigarettes
    - Enrolled in 5 Call OKHL program
    - Willing to quit cigarettes in the next 30 days
    - TCPA consented (consents to outbound telephone calls)

- Not enrolled via Proxy
- None of the following Use Exclusions (UEs) if screened for NRT during first coaching call (if not screened for NRT during first call and eligible the following questions will be asked in the additional screening questions):
  - No heart attack, stroke, or TIA within the past two weeks
  - No rapid or irregular heartbeat in the past 6 months that required a change in activities or medications to treat
  - No angina or heart pain in the past 6 months that a healthcare provider informed participant was serious or worsening
- Did not report a diagnosis of Schizophrenia
- Not previously screened for study
- The GM/RA will make up to 5 call attempts on different days to reach participants identified in the report to complete screening for Phase 1. After 5 attempts to reach the participant, the participant is considered ineligible for the study and will continue with the standard OKHL services they are already enrolled in.
- If a participant completes their second coaching call before the GM/RA is able to reach them to offer study participation, the participant will no longer be eligible for the study.
- For those who are reached, the RA/GM will offer the study via study invitation scripting (*see attachment A: Study invitations*) and ask additional screening questions (*see attachment B: Additional Screening Questions*). All participants who decline or screen out based on additional screening questions will continue with standard OKHL services and will not continue with the study.
- For those who accept the study invitation and are screened as eligible, the GM/RA will read verbal informed consent (*See Attachment C: Study Consent*) and record consent response. Those who decline consent will continue with standard OKHL services.
- For those who consent to the study, the GM/RA will ask the baseline survey questions (*see attachment D: Study Baseline*) and record their answers. They will then be considered enrolled into the ENDSmoking study.
- Once the Baseline survey is completed the GM/RA will attempt to transfer the participant to a study coach for their first study coaching call. If the participant does not have time or a coach is not currently available, the GM/RA will inform the participant that a study coach will be contacting them in the next 24-48 hours to complete their first study coaching call.
- RA will then send out a copy of the verbal consent form that was read to the study participant along with welcome letter (*see attachment G\_ Welcome Letters*) and send the participant a \$20 gift card for completing the baseline survey.
- The RA will also email the participant instructions for completing daily surveys. Participants will either (1) download a smartphone app which they will use to complete the daily survey, or (2) receive an email each day to complete their survey. The smartphone app may not be available for all Phase 1 participants. We will start using the app once our collaborators have successfully made it available in the app store (targeted for May 2018).

**Treatment Plan/Intervention:**

- All calls with participants will be completed by 2 Coaches that have been trained to deliver the study intervention.

- Each participant will receive their standard Oklahoma Tobacco Helpline Nicotine Replacement (NRT) benefit. This is based on insurance status information participants provided when they enrolled.
- The study is not providing any additional NRT. The study does not provide any e-cigarettes.
- Each participant will receive up to 5 outbound coaching calls. Participants can call in for additional support as needed.
- Each participant will be mailed 2 specialized E-Cigarette Quit Guides in addition to the standard OKHL quit guide.
- In every call, the Coach will:
  - (1) Assess participant's cigarette, e-cigarette, and quit medication use and habits.
  - (2) Provide tailored education and behavioral support for individuals who choose to use e-cigarettes while quitting smoking (*see Attachment E: Intervention Protocol Documents*).
- Coaches will receive training and will be guided by Intervention Protocol documents to determine what to cover in their calls with participants.

### **Daily Surveys:**

- Participants will complete daily surveys for a total of 12 weeks after they enroll in the study.
- Daily surveys will be sent via daily emails with a link to a Datstat survey where the participants will fill out the survey online.
- When the study app is available (targeted for May 2018) for participants to download. RA will email each participant with the link to the google store to download the app to their personal phones along with instructions. Participants will be given an option to complete daily surveys through the App or continue to receive daily emails. (see Phone App section below for more details on phone app)
- Participants will be sent 1 survey per day. Daily surveys will take about 1 minute to complete.
- Daily surveys will be sent for 12 weeks.
- Once per week, participants will be sent a slightly longer survey (~3 minutes to complete) to complete in addition to their daily questions.
- Participants will receive gift cards for completing daily surveys.
  - Participants will receive the following incentives for completing daily surveys:
    - \$5 per week for completing at least 5 of 7 daily surveys for the given week. Participants can also receive the \$5 for the week if they complete the longer weekly survey. Or, if participants complete the Timeline Follow-Back interview (see below), they can also receive \$5 for the week.
    - A total possible amount of \$60 can be earned by completing all 12 weeks of daily surveys
    - Participants will also receive a bonus gift card if the participant completes the following percentage of daily surveys:
      - \$50 – completes 80% or more of daily surveys
      - \$25 – completes 60% -79% of daily surveys
      - Those that complete less than 60% of daily surveys will not receive the bonus gift card.
  - Participants will be sent their gift card(s) for daily survey completion at the following times:
    - 7 week – includes surveys completed for weeks 1-6.

- 13 Week – includes surveys completed for weeks 7-12. This gift card will also include the \$50 or \$25 bonus based on the percentage of surveys completed, if earned.
- See Gift Card protocol for details on how Gift Cards will be delivered to participants.

**TimeLine Follow Back (TLFB) Interview:**

- Participants that do not complete (1) at least 5 of 7 daily surveys per week OR (2) the longer weekly diary will be contacted by the RA to complete a TLFB survey over the phone.
- The RA will make up to 3 attempts on different days to reach participants to complete the TLFB survey.
- See TLFB questions (*see attachment J: Study Measures*).

**Follow Up Surveys:**

Research staff will perform the following steps to complete follow up surveys with study participants:

1. Three days before their follow-up survey calls will start, Research Assistant (RA) will email participants to inform them that they will be called to complete the follow-up survey using **Email Reminder #1** (*See attachment H: Study Emails*). This email will include a link to complete the survey online.
2. RA will then begin to call out to participants to complete the survey over the phone at 7 weeks post enrollment for phase 1 and 11 weeks post enrollment for Phase 2.
  - a. If reached, RA will complete phone survey with participant and record responses.
    - i. For those who are selected to complete Qualitative interview:
      1. At the end of the survey RA will schedule with the participant when they will be contacted to complete their Qualitative interview.
    - b. If not reached, RA will make at least 4 more attempts to reach participant for a total of at least 5 attempts on different days. RA will leave a voicemail for participants to call the RA back.
3. If participant is not reached for the phone survey, the RA will email the participant using the **Email Reminder #2** email template (*See attachment H: Study Emails*). A link to complete the survey online will be included in the email.
4. If participant completes an online survey, the RA emails the study participant informing them that we have received their completed survey using the **Email Reminder #3** template (*See attachment H: Study Emails*).
  - a. RA will send gift card to participant.
  - b. If participant reports that they have quit smoking for 7+ days in Phase 2 and for all Phase 1 participants: RA will mail iCO monitor and include instructions on how to use the iCO monitor with the study phone app.
5. RA will check voicemails to see if any study participants have called back to complete survey over the phone.
6. If RA has still not received a completed online survey or phone survey from a participant after 1 month, the RA will send out **Email Reminder #4** (*See attachment H: Study Emails*), which includes a link to a shortened 3 question follow-up survey (see measures document) including only key outcomes of interest.

**Phone App:**

- We will use an android app created by the mHealth Core in the Oklahoma Tobacco Research Center at the University of Oklahoma Health Sciences Center.

- Research staff will program the diary questions into the study app.
  - The phone app will be designed for the following:
    - Ability to complete daily surveys.
    - Ability for participants to connect iCO Smokerlyzers to android smartphone.
      - The iCO Smokerlyzers will provide remote carbon monoxide readings for verification of quit status.
  - The phone App will be free for participants to use and only those enrolled into the Project ENDSmoking study will have access to the app.
- Not all phase 1 participants will begin the study using the phone app. The phone app will approximately be ready in the Google appstore for download in May 2018.
- For participants who enroll into the Phase 1 prior to the app being ready:
  - Research staff will call out to participants once the app is ready for download to introduce them to the phone app and inform them that they study would like them to download the app.
    - Staff will give the participant a choice on whether they would like to complete their daily surveys via the phone app or continue with the emailed surveys.
  - Research staff will then email the participant using Study App Email Instructions (for those who enrolled prior to appstore) template (*See attachment H: Study Emails*). This email will provide them the link to download the app and instructions on how to use the app.
- For participants who enroll into Phase 1 with the app ready for download:
  - Research staff will introduce participants to the phone app during their baseline.
  - After participants enroll in the study, research staff will send an email providing instructions for how to download and set up the app for completing daily surveys.
- After participants complete their follow-up survey, research staff will send an email with instructions on how use the iCO Smokerlyzer with their app and smartphone. The iCO Smokerlyzer will also be mailed to study participants with the instructions.

#### **iCO Monitors/Smokerlyzers®:**

- Research staff will purchase iCO™ Smokerlyzers® monitors from Bedfont Scientific Ltd. These will be used to test whether or not participants have quit smoking.
- All 10 participants in Phase 1 will be sent iCO™ Smokerlyzers® after they complete their follow up survey. All participants will receive the iCO™ Smokerlyzers® to pilot these procedures and receive more feedback from study participants in preparation for Phase 2.
- Participants will be sent instructions via email and mailed with the iCO Smokerlyzer on how to use the device and connect it to the study App.
- When participants receive the iCO Smokerlyzers they will be asked to attach the CO monitor the their phone jack and breath into the monitor several times to record a reading. They will be asked to do this for a total of 3 days to get a reliable assessment of participant’s current smoking status.

#### **Qualitative Interviews:**

- All 10 participants will be contacted to complete a qualitative interview. Findings will be used to improve the intervention development plan for Phase 2 (*see attachment J: Study Measures*)
- Interviews will be designed to collect the following from participants:
  1. ENDS, NRT, and nicotine beliefs (relative harm, safety, long-term use)
  2. Quit strategies used and how and why ENDS were used during the program,

3. Reactions to Shared Decision Making model for quit plan development,
4. Use of and reactions to print materials,
5. Reactions to coaching calls and education from quit coaches
6. Why/why not callers would recommend the program and recommendations for improvement
7. Diary completion experiences.

### **Gift Cards**

- Study Incentives:
  - Both Groups will have the opportunity to receive:
    - Completion of baseline survey - \$20
    - Completion of Daily Surveys - \$5 per week for completing at least 5 of 7 daily surveys per given week. For a total possible amount of \$60 for the 12 weeks
    - Bonus payment for completion of surveys during the 12 weeks:
      - 80% or more - \$50
      - 60-79% - \$25
    - Completion of follow-up survey - \$50
    - Completion of iCO™ Smokerlyzer® test - \$50
  - 10 participants in each phase (Phase 1 & 2) will complete Qualitative Interviews with Study Staff:
    - Qualitative Interview - \$50
  - In total, participants will have the opportunity to earn up to \$280.00 for completing study surveys.
- Participants will get paid by pre-loaded gift cards. During their baseline survey participants will choose which delivery method they would like all of their gift cards to be sent.
  - Delivery Options:
    - Electronic gift cards – sent via email
      - These gift cards are digital, and Participants can only use them online.
    - Mailed gift cards – sent through USPS postal mail
      - These cards are plastic can be used online or at a store.
- Gift Card Delivery Schedule:
  - \$5 week survey completion incentives:
    - Participants will be sent their \$5 week gift card for completing daily survey each week at week 7 and week 13. Gift cards will include both the a total earned for those two time frames:
      - Sent week 7: Weeks 1-6 surveys
      - Sent Week 13: Weeks 7-12 surveys
    - 12 Week Survey Bonus Incentives:
      - Participants will be sent their gift card for completing X% at the end of their 12 weeks.
    - Follow-Up and Qualitative:
      - Participants will be sent their gift card once the study staff completes or receives their respective survey/interview.
    - iCO Smokerlyzer test:
      - Participants will be sent their gift card once study staff receives their iCO results.
- Sending Gift cards:

- Study staff will use the email address or mailing address that was provided during participant's baseline survey for all gift cards.
- Participants are responsible and informed during baseline to call study staff in order to update their email address or mailing address.
- Study staff will send gift cards to participants in the delivery option participants selected during their baseline.
- Troubleshooting gift cards:
  - Participants who have issues with their gift cards can contact study staff or the contact number provided with their gift card.
  - Once gift cards are sent either digitally or mailed, study staff cannot re-issue a gift card.
  - Lost Electronic gift cards:
    - Study staff will assist participants by recommending that the participant search their inbox for their gift card.
  - Stolen Mailed Gift Cards:
    - Study staff will check in with the participant over the phone to see if they would like to provide a different mailing address for the study to use that may be more secure.

**Withdrawal Protocol:**

- If a participant informs the Quit Coach that they no longer wish to participate in the ENDSmoking Study, the Coach will first clarify if they want to withdraw from the study or the quitline treatment (not receive any more coaching calls; participant has the option to opt back in at a later date). If the participant says they want to withdraw from the quitline, but not the study, the Coach will place the participant's file on a status that will prevent the quitline from calling out to the participant, but the participant will still be eligible for study surveys and incentives.
- If the Participant states that they want to withdraw from the study, the Coach will explain that someone from the study will contact them to complete official withdrawal. The coach will also provide the contact information for the study team. Until the participant speaks to the study team to withdraw, they will still be considered part of the study.
- The study team will make five attempts on separate days to call out to participant(s) confirm that the participant wants to withdraw from the study and collect reasons for withdrawal. If the research team member reaches the participant, they will read the following Withdrawal Script (*see attachment 1: Withdrawal Script*).

**Phase 2:**

We are requesting a Waiver of HIPAA Authorization to identify eligible participants among enrollees in the Oklahoma Tobacco Helpline. When individuals call into the Oklahoma Tobacco Quitline (OKHL) and begin their enrollment they will be identified as eligible based on initial eligibility criteria that is collected during their standard OKHL enrollment process. Those who are identified as eligible will be read a brief study offer.

Interested and eligible participants will be screened, consented, and take a baseline questionnaire over the telephone. Participant responses will be recorded in password protected electronic systems. Because recruitment, intervention delivery, and follow-ups are all conducted over the phone,

electronically, or through mailed materials, we are not collecting a signed consent or HIPAA Authorization.

Phase 2 is a randomized pilot study where up to 130 dual users of cigarettes and e-cigarettes will be randomly assigned to receive OKHL treatment as usual or the study intervention treatment that has been tailored for users of e-cigarettes who want to quit smoking cigarettes. Our target is to have 50 callers in each group who engage in at least one session of treatment. Because this is a small sample pilot study where we want to examine the utility of the treatment for those who engage, if a caller does not complete their first treatment call after at least 5 attempts have been made to reach and complete Call 1, the participant will be withdrawn from the study and notified that they are no longer in the research study. These participants will receive coaching support from the OKHL.

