**Randomization:**

- After consent and baseline, the participant will be randomized (*see Study scripts*) into the study at which time they will be considered enrolled into the study. Randomization will be stratified by gender so that equal proportions of males and females are randomized into each treatment arm.
- Following randomization, participants will complete their first coaching call with a coach trained for the group the participant was placed in.
  - If no coach is available, participant will be called back and 5 attempts to reach participant for their Call 1 will be made. If participant is not reached after 5 attempts they will be ineligible for the study and will continue with standard OKHL services.

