**Treatment Plan/Intervention:**

**Group 1 – Control**

- Control group participants will receive 4 additional outbound coaching calls after they complete their initial coaching call, for a total of 5 calls. Participants can call in for additional support as needed. Participants may also be eligible for free nicotine replacement therapy through their standard OKHL benefits. Each participant will receive the standard OKHL quit guide.
- Coaches not trained in the study intervention will complete coaching calls with these participants.

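### Randomised participants who miss Call 1 are withdrawn and the SAP names no analysis set, so the denominator for calls completed, the first primary outcome, is undefined

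*Protocol*

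**What the plan says.** **Order of events.** Under Randomization in the Phase 2 protocol, participants are randomised after consent and baseline "into the study at which time they will be considered enrolled into the study". Call 1 comes next, with a coach assigned to the allocated arm. "If no coach is available, participant will be called back and 5 attempts to reach participant for their Call 1 will be made".

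**Removal rule.** The opening Phase 2 section of the protocol says of callers who never take up that call: "the participant will be withdrawn from the study and notified that they are no longer in the research study". The rule takes effect "after at least 5 attempts have been made to reach and complete Call 1". Randomization describes the same people as ineligible: "If participant is not reached after 5 attempts they will be ineligible for the study and will continue with standard OKHL services". Afterwards, "These participants will receive coaching support from the OKHL".

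**Sample target.** The protocol randomises up to 130. "Our target is to have 50 callers in each group who engage in at least one session of treatment". The reason it gives is that a small pilot should examine how useful the treatment is for people who take it up.

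**Coaches.** Control calls are given by a separate pool: "Coaches not trained in the study intervention will complete coaching calls with these participants". Group 2 – Experimental assigns all its calls to a small trained team.

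**SAP.** Section 2.3c plans 100 randomised 1:1, with the first call given at once. The first primary hypothesis in section 2.4d is that EEC participants complete at least as many calls as TAU participants. The same section plans engagement summaries with CIs, by-group cross-tabulations, and an exploration of group differences in engagement. It names no analysis set and does not refer to the withdrawal rule. Its Sample Size/Power paragraph expects 35 per group with 3-month outcomes after 30% loss.

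**The concern.** Not completing Call 1 is part of the outcome that the first primary hypothesis compares. A rule that removes people for having no calls takes out nearly every zero. The one exception visible in the protocol is someone who leaves the quitline but stays in the study before Call 1 (Withdrawal Protocol). A comparison among those who remain describes how many further calls starters take. It says nothing about how many people started.

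That matters for a hypothesis of at least as many calls, because an arm that starts fewer people can still look equal among starters. Engagement is a main feasibility result for deciding on a larger trial, and the pilot relies on estimates and CIs for that decision. An estimate without a defined denominator is a weak basis for it.

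The removal happens after allocation and depends on reaching a coach from an arm-specific pool, so it could occur at different rates in the two arms.

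**Working it through.** **1. The plan's own figure.** SAP 2.3c: 100 randomised, 1:1, so 50 per group. SAP 2.4d: 30% loss. 50 × (1 − 0.30) = 35 per group, as stated. In the SAP, then, 35 is 70% of those randomised.

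**2. The protocol's figures.** Up to 130 randomised (65 per arm if even) and a target of 2 × 50 = 100 starters. At the ceiling with the target just met:
- withdrawn: 130 − 100 = 30, and 30/130 = 23.1%;
- starting: 100/130 = 76.9%.

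The figure of 130 is a ceiling. If, say, 110 were randomised to obtain 100 starters (an assumption), 10/110 = 9.1% would be withdrawn.

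**3. What 35 would then mean.** If 35 is 70% of 50 starters, it is 35/65 = 54% of those randomised at the ceiling. If 70% applies to all randomised, it becomes 65 × 0.70 = 45.5 per arm. This joins the SAP's loss rate to the protocol's ceiling. Neither document does so, and the gap shows only that the denominator needs stating.

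**4. Effect on mean calls.** With 0 calls for non-starters,

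mean among all randomised = mean among starters × proportion starting.

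The ratio of the starters' mean to the all-randomised mean is therefore number randomised / number starting, whatever the mean itself:
- 130/100 = 1.30, or 30% higher among starters;
- 110/100 = 1.10, or 10% higher.

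**5. What a starters-only comparison can hide.** The documents give no start rates by arm, so these are assumed: 82% start in one arm and 72% in the other, in either direction, with equal means among starters. The ratio of all-randomised means is 0.72/0.82 = 0.878. One arm has 12% fewer calls among all randomised and 0% fewer among starters.

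**6. Precision.** With 65 per arm and 77% starting in each, the 95% CI half-width for the difference in Call 1 completion is 1.96 × √(2 × 0.77 × 0.23 / 65) = 0.145, or about 14.5 percentage points. The assumed 10-point gap lies within that.

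**The case against.** Four points can fairly be made for the plan.

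- **No sentence excludes withdrawn people from analysis.** This stands. Leaving the study is not the same as leaving a denominator, and the SAP read alone leans towards all randomised. A reader might infer that the plan prescribes a starters-only analysis; the documents do not say so. The withdrawal rule and the starter target point that way, the SAP's 100 randomised points the other way, and nothing decides between them.
- **The focus on people who take up treatment is deliberate and disclosed.** This also stands, and it justifies a starters analysis. For that question the starters' mean is not wrong; it answers a different question from the all-randomised mean. It does not justify using starters as the only set for comparing engagement, because starting is part of engagement.
- **Engagement by group is already planned.** True, but none of the planned summaries names Call 1 completion or fixes the denominator. The missing-data methods do not fill the gap: they deal with missing values and non-responders, whereas the call count of someone who never started is known and is zero.
- **The pilot is not powered, and the rates are assumed.** Correct. A reader might infer that the arms will be biased against each other, or that a significant difference will be lost. Neither is supported: separate coach pools make differential removal possible, not shown, and a 10-point gap would fall within the pilot's imprecision.

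**Conclusion.** The point holds as a gap in definition. A stated rule removes randomised participants on the basis of the outcome to be compared, the SAP takes no account of it, and the two documents imply different denominators. If withdrawn participants are left out, the comparison of calls completed is conditional on having taken a call and cannot show an arm difference in starting treatment.

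At the protocol's ceiling with its target just met, 23% of those randomised would be withdrawn and the starters' mean would be 30% above the all-randomised mean. With fewer randomised for the same 100 starters, both figures shrink. The 30% concerns the level of the mean in the pooled sample. Any effect on the difference between arms depends on start rates by arm, which the documents do not give. What is at risk is an undefined and possibly unreported estimate. It should be fixed before analysis because the correction is cheap.

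**What to change.** In SAP 2.4d:

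1. Make all randomised participants the primary set for calls completed, and score 0 for those withdrawn without Call 1. SAP 2.3b (Treatment Adherence/Engagement) says that call completion is captured routinely, so no extra follow-up is needed. Count calls up to the withdrawal decision, with the same rule in both arms. The cut-off is needed because withdrawn people go on to helpline coaching, which for controls resembles their allocated treatment. Use of these records is subject to the consent, which is not among the documents reviewed.
2. Report the proportion completing Call 1 in each arm, and the difference, with 95% CIs.
3. Keep participants with at least one call as a labelled secondary set for calls completed, and as the set for satisfaction and quit-plan ratings.
4. Reconcile 100 randomised (SAP 2.3c) with up to 130 randomised and 50 starters per group (protocol, Phase 2), and state which denominator the 35 per group refers to.

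The cost is SAP wording, a check of the consent and a small amount of extra analysis. The mean number of calls will look less favourable than among starters alone.
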